Efforts targeting the plight of critically ill patients and their informal caregivers have produced mixed results for improving EoL care and informal caregiver mental health. ¹⁰⁻¹² In a recent study of a palliative-care intervention in the ICU designed to reduce caregiver anxiety and depression, PTSD symptoms actually *increased* for those caregivers who received the intervention. ¹² *A primary limitation of these interventions is that they have targeted mental health outcomes but were not explicit mental health interventions.*

We propose here a proof-of-concept study to address this limitation. In response to requests by the directors of the NYPH Medical ICU (MICU), [name] and [name], to address the emotional distress of surrogate decision-makers, we have developed a mental health intervention for surrogate decision-makers of patients in the ICU. We aim to develop further and pilot test this brief mental health intervention called "Enhancing & Mobilizing the POtential for Wellness & Emotional Resilience among Surrogate Decision-Makers of ICU Patients" (EMPOWER) that can be delivered by a trained mental health provider to patient surrogate decision-makers in the ICU. EMPOWER is a cognitive-behavioral, acceptance-based intervention designed to reduce "experiential avoidance"^{3,13} of unpleasant thoughts and feelings related to thinking about the patient's death. EMPOWER targets symptoms of peritraumatic stress and anticipatory grief to reduce experiential avoidance that interferes with optimal decision-making on the patient's behalf. It consists of discrete ~15minute modules that can be delivered flexibly in a setting with multiple interruptions and unexpected crises. The intervention can be delivered in-person or via telehealth. By reducing surrogate decision-makers' experiential avoidance, EMPOWER removes a barrier to ACP, including the completion of advance directives, such as Do Not Resuscitate (DNR) orders. It also is expected to promote the receipt of EoL care consistent with patient values. In this way, EMPOWER should improve EoL care that enhances patient quality of life while also empowering surrogate decision-makers to cope with a loved one's impending death and adjust following the patient's ICU death or discharge. Specifically, we aim to:

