Adult Surrogate Post-intervention Assessment (T2): PG-12 (if patient is alive); FOLLOS (if patient is alive); PG-13 (if patient is deceased); ²⁴ ^{25,26} PDI; PDEQ; IES-R; BEAQ; STAI; DTS revised version; Caregiver Self-Efficacy in the ICU Scale; DRS - EMPOWER; Regret Assessment; Post-Intervention Satisfaction Questionnaire (PISQ).

Adult Surrogate 1 Month Post-T2 Assessment (T3): PG-12 (if patient is alive); FOLLOS (if patient is alive); PG-13 (if patient is deceased); PDI; IES-R; BEAQ; STAI; PHQ-9; DTS revised version; Critical Care Family Satisfaction Survey- EMPOWER; CEQUEL-R (if patient is alive); CEQUEL ²³ (if patient is deceased); Quality of Life (if patient is alive); Quality of Death (if patient is deceased); DRS - EMPOWER; Regret Assessment; Medical Information Update

Adult Surrogate 3 Months Post-T2 Assessment (T4): PG-12 (if patient is alive); FOLLOS (if patient is alive); PG-13 (if patient is deceased); PDI; IES-R; BEAQ; STAI; PHQ-9; DTS revised version; CEQUEL-R (if patient is alive); CEQUEL (if patient is now deceased, but was alive at T3); Quality of Life (if patient is alive); Quality of Death (if patient is deceased); DRS - EMPOWER; Regret Assessment; Medical Information Update; Qualitative Exit Interview for (participants receiving EMPOWER intervention only).

Pediatric Surrogate Assessments: STAI, PDI, PG-12, IES-R, DRS-EMPOWER at all 4 timepoints, with brief demographics at T1, Post-Intervention Satisfaction Questionnaire at T2, and Qualitative Exit Interview at T4 (for participants receiving EMPOWER intervention only).

Measure Title	Time Points Used*	Description of Measure
McGill Quality of Life Scale	Screener	Items 5 through 8 are used to measure anxiety/depression.
Partner Dependency Scale (PDS)	Screener	Items 1 and 2 of the PDS are used to measure dependency. The language is altered to refer to the patient rather than a spouse.
Columbia Suicide Severity Rating Scale	Screener	Items 1 and 2 of the CSSRS are used to measure suicidal ideation.
Peritraumatic Distress Inventory (PDI) ICU Version	T1, T2, T3, T4	Measures peritraumatic distress.
Peritraumatic Dissociative Experiences Questionnaire (PDEQ) ICU Version	T1, T2	Measures experiences of dissociation that may occur in the ICU. Instructions are changed to prompt the participant to specifically answer the survey in reference to their experience in the ICU.
Impact of ICU Events Scale- Revised (IES-R)	T1, T2, T3, T4	Measures symptoms of PTSD.

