We will compute descriptive statistics to characterize the feasibility and acceptability of EMPOWER by examining helpfulness/satisfaction ratings, rates of recruitment, reasons for refusal, and number of modules/booster calls completed. Targets will include completion of 4/6 modules for feasibility and tolerability. Target acceptability will be an average score greater than 3 on the acceptability items in the post-intervention satisfaction questionnaire among participants who received EMPOWER. Tolerability will also be measured by open ended-responses to qualitative questions asked at T4 regarding negative experiences, emotional difficulties, and perceived costs and benefits of participating in the intervention. Drop-out will not be considered as a metric of tolerability due to the highly stressful and variable circumstances of ICU caregiving, unless participants drop out of the study and specifically express that they consider it to be too distressing. Qualitative data analysis will be used to analyze data from open-ended questions to identify the most helpful components of EMPOWER.

To evaluate the preliminary effects of EMPOWER among participants in the combined RCT and COVID-19 open trial phases, we will use a hierarchical linear modeling (HLM) and an intent-to-treat approach. HLM is statistically appropriate because of the clustering within interventionists and within surrogate decision-makers. HLM will correct for this clustering by modeling interventionists and surrogate decision-makers as random effects, as has been done in prior trials ^{38 39}. This will also provide a treatment assignment model coefficient and effect size estimate for our future, larger study.

HLM modeling will determine differences between surrogate decision-makers and patients assigned to EMPOWER vs. enhanced usual care. The primary outcome is post-intervention (T2) differences in PDI scores. Secondary outcomes are differences in scores on the PGD 12/13 and BEAQ at one-month (T3) and three-month (T4) follow up from T2. Exploratory outcomes are differences in scores on the IES-R, STAI, PHQ-9 and Decision Regret Scale at one-month (T3) and three-month (T4) follow up. HLM models will include covariates, either as fixed-effect or time-varying, if those variables are found to be significantly statistically associated with both intervention assignment and the outcome examined.

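### The covariate rule can admit follow-up variables that EMPOWER has changed, in which case the arm coefficient is no longer the intent-to-treat effect

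*Combined protocol and SAP*

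**What the plan says.** In section 6.1 Data Analysis Plan, under Specific Aim #2, the preliminary effects are to be estimated as follows: "we will use a hierarchical linear modeling (HLM) and an intent-to-treat approach". For the main comparison, "The primary outcome is post-intervention (T2) differences in PDI scores". The covariate rule is: "HLM models will include covariates, either as fixed-effect or time-varying, if those variables are found to be significantly statistically associated with both intervention assignment", and also with the outcome being modelled. The section gives no list of candidate covariates, no restriction to T1 values and no exclusion of variables that treatment could affect. Of the fitted model the plan says: "This will also provide a treatment assignment model coefficient and effect size estimate for our future, larger study".

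Section 5.1 Measures Used shows what is collected after assignment. The adult T2 battery includes "PDI; PDEQ; IES-R; BEAQ; STAI; DTS revised version; Caregiver Self-Efficacy in the ICU Scale". Most of these are repeated at T3 and T4. Surrogates of pediatric patients complete a shorter set that includes STAI and IES-R but not BEAQ, PDEQ or DTS.

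Section 1.1 Introduction describes the intended action: "EMPOWER targets symptoms of peritraumatic stress and anticipatory grief to reduce experiential avoidance". It adds that, by doing so, "EMPOWER removes a barrier to ACP, including the completion of advance directives".

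**The concern.** T1 is the only pre-intervention assessment, so a time-varying covariate in this design carries values from T2, T3 or T4. Among randomised participants, a follow-up variable that is truly associated with arm has been changed by the intervention. If it is also associated with the outcome, it is a mediator, a consequence of the outcome, or another effect of treatment. The two significance tests therefore tend to pick out the variables that should stay out of an intent-to-treat model. The rule is worded as a requirement once both tests are met.

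At stake is the arm coefficient for PDI at T2 and for the later outcomes, and the effect size meant to inform the larger trial. A coefficient conditional on a variable that EMPOWER has changed does not estimate the total effect of assignment.

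**Working it through.** **The plan's own figure.** Section 6.1 Statistical power and sample size considerations gives about 80% power for d = 0.75 at alpha 0.05, at 30:30 and again at 40:20. Sidedness is not stated; two-sided is assumed here. The noncentrality is d × √(n₁n₀/(n₁+n₀)).
- 30:30: 0.75 × √(900/60) = 2.905. Power is 82.8% by the normal approximation and 81.5% by the noncentral t.
- 40:20: 0.75 × √(800/60) = 2.739. Power is 78.2% (normal) and 76.8% (t).

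The first figure reproduces. The second reproduces within 2 points by the normal approximation. The covariate rule has no figure of its own.

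**Effect of adjusting.** Take an outcome SD of 1 within arm and a total benefit of 0.75. Let a follow-up covariate M, with within-arm SD 1, be shifted by a in the direction of benefit, with within-arm correlation ρ with the outcome. The adjusted arm coefficient is then

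0.75 − a × ρ.

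- If a share s of the effect runs through M, then a = s × 0.75/ρ and the coefficient is 0.75 × (1 − s).
- If M is only a consequence of the outcome, then a = 0.75 × ρ and the coefficient is 0.75 × (1 − ρ²).

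The documents give neither a nor ρ, so both are assumptions.

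**Effect of the rule.** In the simulations M enters only if p < 0.05 against arm and p < 0.05 against outcome. They use one time point and a linear model, at 30:30 and 40:20, with several thousand runs per setting. Unadjusted power in these runs is about 75–82%.

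| Assumption | Shift a (SD) | Coefficient if M is adjusted for | M passes the rule | Mean estimate under the rule | Power under the rule |
|---|---|---|---|---|---|
| One tenth mediated, ρ 0.5–0.6 | 0.13–0.15 | 0.68 | – | 0.72–0.73 | loss of about 1 point or less |
| Weak link, ρ = 0.3 | 0.30 | 0.66 | 17–18% | 0.71 | 73% (40:20), 78% (30:30) |
| One quarter mediated, ρ 0.5–0.6 | 0.31–0.38 | 0.56 | 21–29% | about 0.65–0.67 | 66–75% |
| Half mediated, ρ 0.5–0.6 | 0.63–0.75 | 0.38 | 61–82% | 0.41–0.46 | 36–47% |

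If BEAQ is downstream of PDI with ρ of 0.5–0.6, the shift is 0.75 × 0.5 = 0.38 to 0.75 × 0.6 = 0.45. The adjusted coefficient is 0.75 × (1 − 0.25) = 0.56 to 0.75 × (1 − 0.36) = 0.48. Together with the quarter-mediated case, the mean estimate under the rule spans 0.58–0.68 SD, with the downstream case at the lower end.

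**Opposite direction.** With a = −0.5 and ρ = 0.5 the adjusted coefficient is 0.75 + 0.25 = 1.00. The simulated mean under the rule is 0.88.

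**Baseline covariates under the same test.** With randomised allocation, a T1 covariate passes both tests in only about 2–5% of trials. The mean estimate stays at 0.75 (0.746–0.752), and power at 40:20 is 77–79%. The harm comes from admitting follow-up values, not from adjustment as such.

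**The case against.** Several points on the other side stand.

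- **No covariate is named.** BEAQ is listed as a secondary outcome, and IES-R and STAI as exploratory outcomes; none is proposed as a covariate. A reader might infer that the plan will adjust away EMPOWER's effect. The documents support only that the rule permits this, and requires it if the two tests are met.
- **BEAQ is not clearly a mediator of PDI.** A reader might take experiential avoidance as the stated route to lower distress at T2. The Introduction puts it largely the other way round: stress and grief are expected to worsen avoidance, and avoidance then obstructs advance care planning. The mediated-share figures do not describe that order. Conditioning on a consequence of PDI still biases the coefficient, as the downstream case shows.
- **The large losses need large shifts.** Half mediated means BEAQ moves by 0.63–0.75 SD, close to the primary effect itself. Three quarters mediated would need 0.94–1.13 SD, more than the primary effect. With a weak link the loss is small.
- **The pooled set is not fully randomised.** The 40:20 split arises from counting COVID-19 open-trial participants, yet the simulations treat it as randomised. In the pooled data a follow-up variable may differ by arm because of phase, so association with arm does not prove that EMPOWER changed it. This supports adjustment for baseline differences, not for values measured after treatment.
- **Patient death matters.** It decides whether PG-12 or PG-13 is scored, so simply deleting the time-varying option would leave that switch unaddressed.

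That this is a pilot does not remove the point, because the plan states a hypothesis on the primary outcome and will carry the effect size forward.

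**Conclusion.** The concern holds as a defect in the rule. Followed as written, the rule can bring variables that EMPOWER has changed into the models that supply the treatment effect. The coefficient then departs from the intent-to-treat effect, usually towards zero and sometimes away from it.

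For a true effect of 0.75 SD, the plausible size runs from a negligible loss to a serious one:
- about 0.72 SD with a weak link, costing roughly 1 to 4 points of power;
- 0.58–0.68 SD if a quarter is mediated or BEAQ is downstream of PDI;
- 0.41–0.46 SD if half is mediated.

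These figures rest on assumed values of the covariate shift and correlation, a single follow-up covariate, complete data, two-sided tests and randomised allocation. They show how far the rule could move the estimate; they do not predict what this trial will find.

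**What to change.** In section 6.1 Data Analysis Plan, limit covariates in every treatment-effect HLM (primary, secondary and exploratory) to a prespecified list of variables measured at or before T1. Examples are the baseline score of the outcome and the baseline characteristics that differ between phases, which are needed because the COVID-19 open trial is not randomised. Keep visit as a design term.

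Drop post-assignment variables from the models that supply the reported effect and the planning effect size. Label any model that contains them as a mediation or sensitivity analysis. Patient vital status may still be used to identify whether PG-12 or PG-13 was scored; state that handling separately.

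The cost is a sentence or two of text. No new data are needed, since the baseline measures are already collected.

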This trial initially proposed to have 15 eligible stakeholders provide feedback about EMPOWER to inform improvements; to enroll 10 initial open trial cases and then to randomize 60 surrogate decision-makers of terminally, critically ill patients who are incapacitated or at risk of becoming incapacitated to EMPOWER or enhanced usual care. Beginning in April 2020, however, to meet the needs of family members in the COVID-19 pandemic, as well as to accommodate recruitment of human subjects with necessary social distancing practices, the RCT phase was paused to enter a new open trial phase (referred to hereafter as the COVID-19 open trial) that did not include randomization or a control arm. Upon approval of amendment #1610017622-13, we will return to the RCT phase. To adhere to recruitment strategies that were originally proposed, the number of participants enrolled in this study will not exceed the 60 participants initially projected, although due to the COVID-19 open trial, over 30 participants total may receive the EMPOWER intervention. Assessments will occur pre-intervention, immediately post-intervention, and then 1 month and 3 months from post-intervention assessment. Results will be used to seek NIH R01 funding for a larger-scale randomized controlled trial (RCT) intervention efficacy study of EMPOWER.

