5.1 Study Design and Methods

5.2 Study Design

There are two phases in this study. The manual refinement phase involves obtaining feedback from stakeholders (bereaved caregivers and clinicians) about the EMPOWER intervention manual using qualitative analysis followed by a modified Delphi method. The second phase involves piloting EMPOWER to obtain information on its feasibility, tolerability, acceptability, and preliminary effect size estimates in order to plan a larger, efficacy RCT. We will conduct an open trial of the intervention followed by a parallel-arm RCT comparing EMPOWER to enhanced usual care. In order to supplement RCT recruitment, adapt to restrictions in ICU visitation and meet the needs of family caregivers impacted by the COVID-19 pandemic, a secondary open trial occurred beginning April 2020, with a return to RCT procedures following approval of amendment #1610017622-13.

Manual Refinement:

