5.1 Measures Used

Measures may be completed using hard copies, online (REDCap), or by RA interview, depending on the respondent's preference and research restrictions due to COVID-19. During the COVID-19 open trial, any hard copies will be mailed, digital copies will be emailed and RA interviews will occur over the phone or other telehealth medium.

Sociodemographic Characteristics:

Demographics: Surrogate decision-makers' will be asked in a self-report assessment occurring either in clinic or over the telephone their own and the patient's age (years), gender, race, education, mental health history, income, marital status, religious/spiritual beliefs, ACP knowledge/understanding, treatment preferences, prognostic understanding, and relationship with patient. Stakeholders will report on their own demographics.

Medical factors for Patients:

Patients' diagnoses (e.g., Stage IV pancreatic or NSCL cancer), reason for hospital/ICU admission, DNR/DNI order status, ACP items (including palliative care consultations), care plans obtained from the medical chart or ICU physicians and fellows, as well as clinically relevant symptoms related to patient incapacity, such as but not limited to, delirium. This information will be compiled as a medical chart abstraction and matched with surrogate-assessed patient treatment preferences assessed at T1 to create a measure of rates of value-concordant care. These medical factors, in addition to the CEQUEL ²³, will serve to measure the outcomes specified in Aim #3.

Psychosocial factors for Surrogate decision-makers:

Screener: Consists of items from 4 items from McGill Quality of Life¹⁹, two items from the Partner Dependency Scale ¹⁸, and two items from the Columbia Suicide Severity Rating Scale ²⁰.

Adult Surrogate Pre-intervention/ Baseline Assessment (T1): Psychiatric History, Demographics, and Treatment Preferences; Prolonged Grief Disorder (PG-12) Caregiver Version; ²⁴ ^{25,26}; Fear of Losing Loved Ones Scale (FOLLOS); Peritraumatic Distress Inventory (PDI) ²⁷; Peritraumatic Dissociative Experiences Questionnaire (PDEQ) ICU Version²⁸; Impact of ICU Events Scale-Revised (IES-R) ²⁹; Brief Experiential Avoidance Questionnaire (BEAQ); ³⁰State Trait Anxiety Inventory - State scale (STAI) ³¹; Patient Health

Questionnaire (PHQ-9); ³² Distress Tolerance Scale (DTS) ³³ revised version; Caregiver Self-Efficacy in the ICU Scale; Decision Regret Scale (DRS) – EMPOWER³⁴; Regret Assessment.

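### Covariates must pass two significance tests to enter the model, and the role of baseline (T1) PDI in the primary T2 comparison is not stated; the cost is mainly lost precision

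*Combined protocol and SAP*

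**What the plan says.** Section 6.1 Data Analysis Plan, Specific Aim #2, gives the only covariate rule. Covariates, fixed or time-varying, enter the model "if those variables are found to be significantly statistically associated with both intervention assignment and the outcome examined". No test or significance level is named.

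The same section defines the primary endpoint: "The primary outcome is post-intervention (T2) differences in PDI scores". The model is fitted "among participants in the combined RCT and COVID-19 open trial phases", with clustering handled by "modeling interventionists and surrogate decision-makers as random effects". It is also meant to supply the effect size for the larger trial. The open-trial phase was one "that did not include randomization or a control arm" (1.1 Introduction).

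Section 5.1 Measures Used lists PDI at T1 to T4 for adult surrogates and at all four time points for paediatric surrogates. No section says whether T1 PDI is a mandatory covariate, a screened covariate, one of the repeated responses, or part of a change score.

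The sample size section projects 40 EMPOWER and 20 enhanced usual care (EUC) participants and claims 80% power for d=0.75 at alpha 0.05.

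**The concern.** A baseline measure of the outcome is usually its strongest predictor, and including it narrows the confidence interval whether or not the arms happen to be balanced. A rule that also demands a significant difference between arms excludes that predictor in most trials where the arms are comparable. It also makes the model depend on the trial's own data.

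The usual reassurance that randomisation balances baselines applies only in part here, because the pooled EMPOWER arm contains participants who were never randomised. The open trial was run to "adapt to restrictions in ICU visitation and meet the needs of family caregivers impacted by the COVID-19 pandemic", so its setting differed from that of the RCT.

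The screen also works badly for time-varying covariates. A post-baseline variable that EMPOWER changes is associated with assignment for that very reason, so it is a favoured candidate. Adjusting for it could remove part of the effect being estimated.

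At stake are the precision and the definition of the estimate that will be used to plan the next trial.

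**Working it through.** **Inputs.** From the documents: 40 vs 20, d=0.75, alpha 0.05 (taken as two-sided). Assumed, because the documents give no value: a 0.05 screening level; T1-T2 correlation r of 0.3, 0.5 or 0.7; 1:1 randomisation, so that 20 of the 40 EMPOWER participants come from the open trial; and an open-trial shift s in T1 PDI of 0 to 1.0 SD. The SD is set to 1. The simulations used 40,000 runs per setting (6,000 to 8,000 for the second and third rows of the step 4 table), one follow-up time point, least squares, no interventionist effect and no missing data.

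**1. The plan's own figure.** SE = √(1/n₁ + 1/n₂).
- 30:30: power is 81.5% by the t-test.
- 40:20: SE = √(0.025 + 0.05) = 0.274, and 0.75/0.274 = 2.74. Power is 78.2% by the normal approximation and 76.8% by the t-test.

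The stated 80% is thus reproduced to within 2 points at 30:30 by the t-test and at 40:20 by the normal approximation, with no baseline adjustment.

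**2. How often the screen drops T1 PDI.** With no true imbalance, the test against assignment is significant in 5% of trials by construction, so about 95% of trials drop T1 PDI before the outcome test is considered. With both tests, the simulated drop rate is about 95-97% over r=0.3 to 0.7. At r=0.5, screens at 0.10 and 0.20 still drop it in 90% and 80%.

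**3. Precision with no shift.** The adjusted SE is approximately 0.274 × √(1 − r²).

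| r | Adjusted SE (formula) | Mean SE, rule / adjusted (simulated) | Ratio | Power, rule / adjusted |
|---|---|---|---|---|
| 0.3 | 0.261 | 0.272 / 0.262 | 1.04 | 77% / 80% |
| 0.5 | 0.237 | 0.272 / 0.238 | 1.14 | 78% / 87% |
| 0.7 | 0.196 | 0.270 / 0.196 | 1.38 | 79% / 96% |

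**4. Bias if the phases differ.** A shift s in half of the EMPOWER arm gives a T1 difference between arms of s/2. What follows depends on how the shift reaches T2. For r=0.5 and s=0.5 (positive means towards no effect, if open-trial surrogates start more distressed; signs reverse if less):

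| Phase difference | Raw T2 difference | Adjusted, by formula | Adjusted (simulated) | Rule (simulated) |
|---|---|---|---|---|
| Acts through T1 PDI | r·s/2 = 0.125 | 0 | about 0 | 0.08 |
| Persists to T2 independently of T1 | s/2 = 0.25 | s/2 − r·s/2 = 0.125 | 0.12 | 0.20 |
| Confined to T1 | 0 | −r·s/2 = −0.125 | −0.12 | −0.04 |

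In the first case, shifts of 0.25/0.5/1.0 SD leave bias of about 0.05/0.08/0.11 SD under the rule. The type I error of the rule was 4-7% in the first-case settings run.

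**5. If T1 PDI is a repeated response.** Step 2 then does not apply. The primary contrast could be the raw T2 difference or the change from T1. These two differ by the T1 difference itself, s/2, whatever the mechanism: 0.25 SD at s=0.5. A third option constrains the arms to a common T1 mean. The text does not choose among them.

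**The case against.** The strongest objection is that the screen may not touch T1 PDI at all. A surrogate random effect needs several responses per person, and PDI is measured four times, so T1 PDI could well be a response. That stands: the drop rates and power losses above hold only if T1 PDI is screened. The alternative reading does not rescue the plan, because it leaves the primary contrast undefined.

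A reader might infer that the rule biases the primary result and that adjustment cures it. The documents do not support this. Adjustment is unbiased only if the phase difference works wholly through measured T1 PDI, which cannot be assumed for people who were never randomised. If the difference is confined to T1, adjustment does worse than the rule.

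A reader might also infer that baseline PDI does differ by phase. No document shows that. Adult screening thresholds are the same in both phases (3.1 Eligibility Criteria). The rule for the open trial, "During the COVID-19 open trial, any hard copies will be mailed, digital copies will be emailed", narrowed a menu of assessment modes that was already open to all participants.

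Finally, this is a pilot seeking preliminary effects, and the bias figures are modest against a standard error of about 0.27. That is fair. It limits the weight of the point but gives no reason to keep a rule that discards precision from data already collected.

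**Conclusion.** The point holds as one of precision and specification, and the change is a free improvement. If T1 PDI is screened at 0.05, it is left out of about 95-97% of trials with no true imbalance. At d=0.75 the plan then has about 77-79% power, where routine adjustment would give 80%, 87% or 96% for correlations of 0.3, 0.5 or 0.7. The gain is small at 0.3 and large at 0.7, and the documents do not give the correlation. If T1 PDI is a repeated response, the defect is instead that the T2 contrast is not defined.

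Bias removal is conditional. At r=0.5 the rule leaves about 0.05-0.11 SD for shifts of 0.25-1.0 SD acting through T1 PDI, and adjustment removes it. Under a persistent shift of 0.5 SD, adjustment lowers the bias from about 0.20 to 0.12 SD. Under a T1-only shift of that size, it moves the bias from about −0.04 to −0.12 SD. Bias should therefore not be the main argument for the change, and the calculations do not support a claim of materially inflated type I error. Pooling never-randomised participants is a separate and larger issue that this change does not cure.

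**What to change.** Replace the significance-based rule in section 6.1 Data Analysis Plan with the following.

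- The T1 value of each outcome, where collected, is a fixed covariate in its model regardless of balance or significance: T1 PDI for the primary outcome; T1 PG-12 for the PG-12/13 outcome; T1 BEAQ, IES-R, STAI, PHQ-9 and Decision Regret Scale for their own outcomes.
- The primary contrast is the adjusted T2 difference in PDI.
- Any other baseline adjustment variables are named in advance, for example site and adult or paediatric patient.
- Post-baseline variables that assignment could affect are not used as adjustment covariates. This does not restrict the choice of PG-12 or PG-13 by patient status.
- The same model is reported in randomised participants only, as a sensitivity analysis, because T1 adjustment cannot remove unmeasured phase differences.
- A model with a common baseline mean is not offered as an equivalent for the pooled analysis, since it imposes equal T1 means that randomisation does not guarantee here. It may be used, with an unstructured covariance, in the randomised-only analysis.

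The cost is SAP wording, about one degree of freedom per covariate and one low-powered sensitivity analysis: at an assumed 20:20, power at d=0.75 is about 67/75/89% for r=0.3/0.5/0.7. No new data are needed.
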